## 8.5.3. Pharmacokinetic Statistical Methodology

All PK concentrations and parameters will be listed.

Summary tables, mean (+ standard deviation [SD]) figures, overlaying individual figures, and individual figures by treatment and time postdose will be provided for plasma PK concentrations. All figures will be produced on both linear and semi-logarithmic scales.

Summary tables by treatment will be provided for all PK parameters, with the exception of regression-related PK parameters.

Page 17 of 47

# **Bioequivalence:**

A statistical analysis will be conducted to investigate the bioequivalence of 960 mg sotorasib administered orally as 3 x 320 mg tablets (test 1) to 960 mg sotorasib administered orally as 8 x 120 mg tablets (reference treatment) for  $AUC_{last}$ ,  $AUC_{inf}$ , and  $C_{max}$ . Data from the entire study population will be used for this analysis.

The natural log (ln)-transformed PK parameters will be analyzed using a mixed model. The model will include treatment, period, and sequence as fixed effect and subject nested within sequence as a random effect.

For AUClast, AUCinf, and Cmax separately, the least squares mean (LSM) for each treatment, difference in LSMs between the test 1 and reference treatments, and corresponding 90% confidence interval (CI) will be calculated; these values will then be backtransformed to give the geometric least square mean (GLSM), ratio of GLSMs, and corresponding 90% CI.

Additionally, the pooled estimate (across all treatments) of the within-subject CV will be calculated, and residual plots will be produced to assess the adequacy of the model(s) fitted.

It will be concluded that the test treatment is bioequivalent to the reference treatment if, for Cmax and AUCs, the 90% CI for the ratio of GLSMs is completely contained within the predefined interval of (0.8000, 1.2500). This procedure is equivalent to Schuirmann's two one-sided tests at the 0.05 level of significance.

Examples of the SAS code that will be used are as follows:

#### **Mixed Model Analysis**

```
proc mixed data = <data in>;
  by parcatln parcatl pkday paramn param;
  class trtan aperiod trtseqp usubjid;
  model lpk = trtan aperiod trtseqp / cl residual ddfm = kr;
  lsmeans trtan / cl pdiff = control('2') alpha = 0.1;
  random intercept / subject = usubjid(trtseqp);
  ods output lsmeans = <data out>;
  ods output diffs = <data out>;
  ods output covparms = <data out>;
run;
```

## **Food Effect:**

A statistical analysis will be conducted to investigate the food effect for 960 mg sotorasib administered orally as 3 x 320 mg tablets under fed condition (test 2) to 960 mg sotorasib administered orally as 3 x 320 mg tablets under fasted condition (test 1) for  $AUC_{last}$ ,  $AUC_{inf}$ , and  $C_{max}$ . Data from 14 subjects who are enrolled in Period 3 will be used for this analysis.

The natural log (ln)-transformed PK parameters will be analyzed using a mixed model. The model will include treatment as fixed effect and subject nested within sequence as a random effect.

For AUClast, AUCinf, and Cmax separately, the least squares mean (LSM) for each treatment, difference in LSMs between the test 1 and test 2, and corresponding 90% confidence interval (CI) will be calculated; these values will then be backtransformed to give the geometric least square mean (GLSM), ratio of GLSMs, and corresponding 90% CI.

Additionally, the pooled estimate (across all treatments) of the within-subject CV will be calculated, and residual plots will be produced to assess the adequacy of the model(s) fitted.

Examples of the SAS code that will be used are as follows:

# **Mixed Model Analysis**

```
proc mixed data = <data in>;
  by parcatln parcatl pkday paramn param;
  class trtan usubjid;
  model lpk = trtan / cl residual ddfm = kr;
  lsmeans trtan / cl pdiff = control('2') alpha = 0.1;
  random intercept / subject = usubjid(trtseqp);
  ods output lsmeans = <data out>;
  ods output diffs = <data out>;
  ods output covparms = <data out>;
run;
```

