## 8.3. Pharmacokinetic Analyses

The plasma PK parameters of sotorasib on Days 1 and 4 will be calculated using standard noncompartmental methods.

The primary PK parameters are  $C_{max}$ , AUClast, and AUCinf for sotorasib on Days 1 and 4. All other PK parameters will be regarded as secondary. A linear mixed-effects model will be used to analyze log-transformed primary PK parameters. The model assumes fixed effect for treatment, period, and sequence and a random effect for subject. Geometric mean ratios for  $C_{max}$  and AUC values and associated 90% confidence intervals (test/reference) will be estimated. The "reference" treatment for PK analysis will be Treatment B while the "test 1" treatment will be Treatment A for the bioequivalence analysis. For the food-effect analysis, the model will use 14 subjects' data and assumes fixed effects for treatment and random effect for subject while test treatment would be fed (test 2; Treatment C) and reference would be fasted (test 1; Treatment A).

Additional parameters may be calculated. Specific details will be presented in the Statistical Analysis Plan for this study.

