#### 6. STUDY TREATMENTS

The study treatment names, abbreviations, and ordering to be used in the TFLs are presented in Table .

Table 1:Presentation of Study Treatments in TFLs

Final Version 1.0, 15Oct2021 Page 8 of 22 ST-AD-031 Version 02

\*Subjects will receive a single dose in each treatment period, on Days 1, 4, and 7.

\*\* Subjects will be discharged on Day 6 or Day 9 according to their treatment assignment.

Treatments	Abbreviation	Order in TFLs
one administration of 960 mg sotorasib administered orally as 3 x 320 mg tablets (Test 1)	Treatment A	1
one administration of 960 mg sotorasib administered orally as 8 x 120 mg tablets (Reference)	Treatment B	2
one administration of 960 mg sotorasib administered orally as 3x 320 mg tablets with a high-fat meal (Test 2)	Treatment C	3

The study treatment sequence names, abbreviations, and ordering to be used in the TFLs are presented in Table 1.

Table 1: Presentation of Study Treatment Sequences in TFLs For all subjects:

Study Treatment Sequence	Abbreviation	Order in TFLs
one administration of 960 mg sotorasib administered orally as 3 x 320 mg tablets on Period 1 (Day 1) and one administration of 960 mg sotorasib administered orally as 8 x 120 mg tablets on Period 2 (Day 4)	Sequence AB	1
one administration of 960 mg sotorasib administered orally as 8 x 120 mg tablets on Period 1 (Day 1) and one administration of 960 mg sotorasib administered orally as 3 x 320 mg tablets on Period 2 (Day 4)	Sequence BA	2

For the 14 subjects attending all 3 periods:

Study Treatment Sequence	Abbreviation	Order in TFLs
one administration of 960 mg sotorasib administered orally as 3 x 320 mg tablets on Period 1 (Day 1) and one administration of 960 mg sotorasib administered orally as 8 x 120 mg tablets on Period 2 (Day 4) and one administration of 960 mg sotorasib administered orally as 3x 320 mg tablets with a high-fat meal (Day 7)	Sequence ABC	1
one administration of 960 mg sotorasib administered orally as 8 x 120 mg tablets on Period 1 (Day 1) and one administration of 960 mg sotorasib administered orally as 3 x 320 mg tablets on Period 2 (Day 4) and one administration of 960 mg sotorasib administered orally as 3x 320 mg tablets with a high-fat meal (Day 7)	Sequence BAC	2

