# 12. APPENDICES

# **Appendix 1: Document History**

Status and Version	Date of Change	Summary/Reason for Changes
		Corrected Pinnacle 21 version:
		Change from:
Final Version 1.0	10Jan2022	Pinnacle 21 Enterprise Version 4.2.1
		To:
		Pinnacle21 Community Validator 3.1.2
	03May2022	SAP page 17 Section Food Effect. Updated wording typo as there's only 1 sequence for Food Effect analysis, there're no subject nested within sequence for the analysis model.
Final Version 1.0		Change: The model will include treatment as fixed effect and subject nested within sequence as a random effect. To:
		The model will include treatment as fixed effect and subject nested within sequence as a random effect.

 $\overline{NA} = not applicable$ 

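### The food-effect example SAS code repeats the bioequivalence control level, which points to Treatment B and not fasted Treatment A, and its CLASS statement omits a variable that RANDOM uses

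*SAP*

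**What the plan says.** Protocol Section 8.3 sets the food-effect model as a fixed treatment effect with a "random effect for subject while test treatment would be fed (test 2; Treatment C) and reference would be fasted (test 1; Treatment A"). For bioequivalence, the same section makes Treatment B the reference.

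The Food Effect part of SAP Section 8.5.3 keeps that comparison. It states that "Data from 14 subjects who are enrolled in Period 3 will be used for this analysis", and that the "difference in LSMs between the test 1 and test 2, and corresponding 90% confidence interval (CI) will be calculated". Its model sentence has treatment as a fixed effect and subject nested within sequence as a random effect.

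The example code for the food effect contains "lsmeans trtan / cl pdiff = control('2') alpha = 0.1", "class trtan usubjid" and "random intercept / subject = usubjid(trtseqp"). The bioequivalence block has the same LSMEANS and RANDOM lines, but its CLASS statement also lists aperiod and trtseqp.

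SAP Section 6 gives the only treatment order in the document: Treatment A is 1, the treatment "administered orally as 8 x 120 mg tablets (Reference") is Treatment B and is 2, and Treatment C is 3. The SAP appears twice in the file, and both copies carry the same food-effect code. The document history in the second copy has an entry of 03May2022 on the food-effect model, saying that "there're no subject nested within sequence for the analysis model".

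**The concern.** The two analyses have different references, yet both code blocks select control level 2. A single level can serve both only if the treatment variable is coded differently in each, and neither document says that it is. If the Section 6 order applies, the food-effect block names Treatment B as control, which is not the comparison that the text promises. Separately, the block uses a sequence variable in RANDOM that CLASS does not declare.

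At stake is whether the code that the SAP says will be used produces the planned fed-versus-fasted ratio and its 90% confidence interval. With B records present, the code would give complete, plausible-looking rows for the wrong pairs, so the slip need not be obvious to a programmer who follows the example.

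**Working it through.** **The plan's own figure.** The point does not depend on the sample size, but the stated figure reproduces. With a within-subject SD of 0.472 on the log scale and 132 completers, SE = 0.472 × √(2/132) = 0.0581 with 130 degrees of freedom. For a true ratio of 0.95, limits of 0.80 and 1.25, and two one-sided tests at 5%, the power is 0.902, against the stated 90%.

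**Step 1: what level 2 means.** The SAP does not define trtan. In the bioequivalence block the control is level 2 and the stated reference is Treatment B, so level 2 must be B there. The order in Section 6 (A = 1, B = 2, C = 3) agrees.

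**Step 2: carry that coding into the food-effect block.** The text limits the subjects to the 14 in Period 3 but does not say whether their Treatment B records are removed. Both cases follow, with residual degrees of freedom = records − subjects − (treatments − 1).

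| Input | Records | Levels present | Residual df after subject | Differences requested by control level 2 | Planned C-A requested? |
|---|---|---|---|---|---|
| A, B and C | 14 × 3 = 42 | 1, 2, 3 | 42 − 14 − 2 = 26 | A-B, C-B | No |
| A and C only | 14 × 2 = 28 | 1, 3 | 28 − 14 − 1 = 13 | None available: level 2 is absent | No |

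In the first case the planned difference equals (C-B) − (A-B), so the model contains it, but this statement does not print it or its interval. In the second case C-A is estimable (design rank 2), but the control level named is not in the data. With level 1 as control and the A and C records, the statement requests C-A, which is the planned comparison.

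**Step 3: codings under which the line would be right.** If trtan were recoded for this analysis with test C = 1 and reference A = 2, control level 2 would be A and the output would be C-A. A two-level recode that kept the order (A = 1, C = 2) would give A-C, the inverse. Neither document states any recode.

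**Step 4: CLASS against RANDOM.** This step does not depend on the coding. RANDOM refers to usubjid within trtseqp, while CLASS lists only trtan and usubjid. The bioequivalence block, with the same RANDOM line, does list trtseqp.

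**Step 5: does the nesting matter?** Each subject belongs to one sequence, so subject and subject-within-sequence define the same 14 groups and the same random-effect covariance. In one simulated data set (14 subjects, seven per sequence, A and C records), both versions gave C/A = 1.278 with a log-scale SE of 0.153. Those values only show that the two fits agree.

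Nothing was run in SAS. The steps rest on the code as printed and on rank and record counts.

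**The case against.** The strongest reply is that the planned analysis is not in doubt. The protocol and the SAP text both name fed C against fasted A, with the difference, ratio and 90% interval. The code is offered as an example with placeholder data-set names, and a programmer would follow the text. This stands, and it is why the point is minor. It does not remove the inconsistency, because the SAP presents these examples as code to be used.

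Second, trtan is undefined, and the Section 6 column is an order for tables and listings, not a code list. A per-analysis coding of test = 1 and reference = 2 would make the line correct in both blocks. The table, figure and listing shells are a separate document that is not available here. This also stands, so the control-level finding is conditional. But the indications that the documents do give point to level 2 being B, and a recode on which the code depends should be stated.

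Third, the RANDOM line follows the SAP's own sentence on nesting, and the SAP says that it supersedes the protocol's statistical considerations. That is correct. The defect is the missing CLASS entry, not the nesting itself.

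Fourth, the document-history entry is weak evidence. Its before and after sentences read the same in the extracted text, possibly because formatting was lost, and its premise of a single sequence does not fit Section 6, which lists ABC and BAC for these 14 subjects. It is used here only as a sign of intent.

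**Conclusion.** The food-effect example code does not agree with the analysis that it illustrates. Under the coding implied by the bioequivalence block and the Section 6 order, it either omits the planned C-A comparison or names a level that is absent. This rests on that coding, which the SAP does not define. The CLASS omission holds whatever the coding.

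The size is minor. The food-effect analysis is secondary and has no decision rule, the contrast in the text is right, and the nesting choice leaves the estimate unchanged.

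A reader might infer that a C/B ratio would be reported as the food effect. The documents do not support that: it would need the B records to be kept, no recode, and the C-B row to be mislabelled against a text that states the right pair. A reader might also infer that the bioequivalence conclusion is at risk. Its control level matches its reference, so it is not. Nor can it be concluded from the undefined BY variable pkday, present in both blocks, that the periods are split. The period term and random intercept in the bioequivalence block suggest that they are fitted together, so that is at most a query.

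**What to change.** In the food-effect code of SAP Section 8.5.3, in both copies:

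- Restrict the input to Treatments A and C in the Period 3 subjects.
- Set the control level to Treatment A, which is `control('1')` under the Section 6 order, or state a separate trtan coding for this analysis.
- Align CLASS, RANDOM and the text in one of two ways. Either add trtseqp to CLASS and keep the nested wording, or use `subject = usubjid` and also delete the nesting from the Food Effect model sentence. The second follows the intent in the document history. If it is chosen, reconcile that entry's single sequence with the two listed in Section 6. Changing the code alone would create a new mismatch with the text.

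The cost is a few edits to one code block and, under the second option, one sentence, each made in both copies. No new data or subjects are needed, and neither the design nor the sample size changes.

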#### 8.6. Safety and Tolerability Assessments

#### 8.6.1. Adverse Events

All AEs will be coded using the Medical Dictionary for Regulatory Activities (MedDRA) Version 24.0 (or higher if a new version is issued during the study; see the DMP for more details). All AEs will be assigned a severity grade using Common Terminology Criteria for Adverse Events (CTCAE) Version 5.0 (or higher if a new version is issued during the study; see the protocol for more details).

A treatment-emergent adverse event (TEAE) will be defined as an AE that starts during or after dosing, or starts prior to dosing and increases in severity after dosing within each period.

A treatment-related TEAE will be defined as a TEAE with a relationship related to the study treatment, as determined by the investigator.

All AEs will be listed. In addition to the data recorded in the database, the listings will include derived onset time and duration. Onset time will be calculated from the time of dosing for TEAEs only.

The frequency of subjects with TEAEs and the number of TEAEs will be summarized for the following categories:

- TEAEs (overall, serious, leading to discontinuation, and leading to death) by treatment
- TEAEs by severity and treatment

• Treatment-related TEAEs (overall, serious, leading to discontinuation, and leading to death) by treatment

• Treatment-related TEAEs by severity and treatment

The frequency of subjects will be summarized separately for TEAEs and treatment-related TEAEs by the following:

- System organ class, preferred term, and treatment
- Preferred term and treatment

For the AE data the following rules will apply:

- For the derivation of treatment-emergent status (applicable to all AEs): If the start date/time of an AE is incomplete or missing, an AE will be assumed to not be a TEAE, unless the incomplete start date/time or the end date/time indicates an AE started after dosing.
- For the derivation of treatment-related status (applicable to TEAEs only): If the study treatment relationship for a TEAE is missing, a TEAE will be assumed to not be a treatment-related TEAE.
- For the derivation of onset time (applicable to TEAEs only): If the start date/time of a TEAE is missing, onset time will not be calculated. If the start date/time of a TEAE is incomplete, where possible, the minimum possible onset time will be calculated and presented in '≥DD:HH:MM' format (eg, if the date/time of dosing is 01MAY2019/08:00 and recorded start date/time of a TEAE is 03MAY2019, then the minimum possible onset time will be calculated by assuming a TEAE started at the first hour and minute of 03MAY2019 [03MAY2019/00:00], thus will be presented as onset time ≥01:16:00 in the listing). If the start date of a TEAE is the same as the date of dosing but the start time of a TEAE is missing, an onset time will be presented as '>00:00:01'. Any clock changes will be accounted for in the derivation.
- For the derivation of duration (applicable to all AEs): If the end date/time of an AE is missing, duration will not be calculated. If the start or end date/time of an AE is incomplete, where possible, the maximum possible duration will be calculated and presented in '≤DD:HH:MM' format (eg, if the start of an AE date/time is 01MAY2019/08:00 and its recorded end date/time is 03MAY2019, then the maximum possible duration will be calculated by assuming an AE ended at the last hour and minute of 03MAY2019 [03MAY2019/23:59], thus will be presented as duration ≤02:15:59 in the listing). Any clock changes will be accounted for in the derivation.
- For the calculation of TEAE summary statistics: If the severity of a TEAE is missing, that TEAE will be counted under the 'missing' category.

Page 20 of 47

• For the calculation of TEAE summary statistics: If a subject experienced multiple TEAEs with the same preferred term for the same treatment, this will be counted as 1 TEAE for that treatment under the maximum severity recorded.

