#### **Recording Adverse Events and Serious Adverse Events**

#### Adverse Event and Serious Adverse Event Recording

- When an adverse event or serious adverse event occurs, it is the responsibility of the Investigator to review all documentation (e.g., hospital progress notes, laboratory, and diagnostics reports) related to the event.
- The Investigator will then record all relevant adverse event/serious adverse event information in the Event electronic Case Report Form (eCRF).
- The Investigator must assign the following adverse event attributes:
  - Adverse event diagnosis or syndrome(s), if known (if not known, signs or symptoms);
  - Dates of onset and resolution (if resolved);
  - Did the event start prior to first dose of investigational product, other protocolrequired therapies;
  - Assessment of seriousness;
  - Severity (or toxicity defined below);
  - Assessment of relatedness to the investigational product(s) and/or studymandated procedures;
  - Action taken; and
  - Outcome of event.
- If the severity of an adverse event changes from the date of onset to the date of resolution, record as a single event with the worst severity on the appropriate eCRF.
- It is not acceptable for the Investigator to send photocopies of the subject's medical records to Sponsor in lieu of completion of the appropriate eCRF page.

- If specifically requested, the Investigator may need to provide additional follow-up information, such as discharge summaries, medical records, or extracts from the medical records. In this case, all subject identifiers, with the exception of the subject number, will be blinded on the copies of the medical records before submission to the Sponsor.
- The Investigator will attempt to establish a diagnosis of the event based on signs, symptoms, and/or other clinical information. In such cases, the diagnosis (not the individual signs/symptoms) will be documented as the adverse event/serious adverse event.

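### SAP 8.6.1 resolves missing adverse-event causality and unresolvable onset toward lower counts: a minor point with a cheap fix

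*SAP*

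**What the plan says.** SAP 8.6.1 defines a treatment-related event by the investigator's judgement and then adds a rule for when that judgement is absent: "If the study treatment relationship for a TEAE is missing, a TEAE will be assumed to not be a treatment-related TEAE". There is no exception.

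For treatment-emergent status, an event with a missing or incomplete start is taken as not emergent, "unless the incomplete start date/time or the end date/time indicates an AE started after dosing".

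Three nearby provisions bear on these rules:

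- Missing severity is handled differently in the same section: "If the severity of a TEAE is missing, that TEAE will be counted under the 'missing' category". SAP 8.1.2 takes the same line for categorical data in general: no imputation unless specifically stated, and a visible category for missing values.
- The onset-time rule contains the clause "If the start date of a TEAE is the same as the date of dosing but the start time of a TEAE is missing", and gives such an event a nominal onset of 00:00:01 in the SAP's day:hour:minute format.
- Protocol Appendix 1 states "The Investigator must assign the following adverse event attributes", and the list includes relatedness and the question "Did the event start prior to first dose of investigational product". The SAP rule on emergent status does not refer to that question.

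**The concern.** Safety and tolerability is a secondary objective, and the adverse-event summaries in SAP 8.6.1 are by treatment. They cover only treatment-emergent and treatment-related events. An event defaulted out of emergent status therefore appears in the listing but in no adverse-event table. An emergent event with no causality assessment stays in the overall table but drops out of the treatment-related one.

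Both defaults err in the same direction. The causality default turns an absent assessment into a favourable one and leaves no trace in the table, although the SAP keeps absent severity visible. The onset default puts the burden on the dates to prove onset after dosing, although a required field may already answer the question for the first dose. At stake is whether the treatment-related and emergent counts, above all in the small fed group, can be read without going back to the listings.

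**Working it through.** **The plan's own onset example.** Dose 01MAY2019 08:00, event dated 03MAY2019 without a time. Minimum onset = 03MAY 00:00 − 01MAY 08:00 = 1 day 16 h = 01:16:00. This agrees with SAP 8.6.1.

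**The onset default on test dates.** Same dose time, no end date recorded. The SAP rule counts an event as emergent only if its earliest possible start is at or after dosing. The alternative counts it as emergent unless its latest possible start is before dosing.

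| Recorded start | SAP rule | Alternative |
|---|---|---|
| Missing | Not emergent | Emergent |
| 01MAY2019, no time | Not emergent | Emergent |
| MAY2019 only | Not emergent | Emergent |
| 02MAY2019, no time | Emergent | Emergent |
| 30APR2019, no time | Not emergent | Not emergent |

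Three of the five change, all from not emergent to emergent. An end date rescues none of these three on a literal reading. It can cap the latest possible start, but it cannot raise the earliest, so it cannot by itself show onset after dosing.

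**The dosing-day clause.** Take an event dated Day 4 without a time. Measured by the minimum-onset method from a Day 1 dose at 08:00, its onset would be Day 4 00:00 − Day 1 08:00 = 2 days 16 h = 02:16:00. The clause gives 00:00:01 instead, so it measures from that day's own dose. That implies attribution to that day's treatment, but only through a rule for displaying onset. No tabulation rule says so. For Day 1 the date alone does not show onset after dosing, so the default makes the event not emergent and the clause is never reached.

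**Size of the causality default.** Denominators: 14 subjects in Period 3 for Treatment C; about 146 enrolled and at least 132 completing for A and B. The documents give no rate of missing causality, so one or two affected subjects is an assumed range. Change = affected subjects / denominator.

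| Affected subjects | C (14) | A or B (146) | A or B (132) |
|---|---|---|---|
| 1 | 7.1 points | 0.7 points | 0.8 points |
| 2 | 14.3 points | 1.4 points | 1.5 points |

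These are maxima. They assume that the event would have been judged related and that the subject has no other related event in that row.

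**The case against.** The case for leaving the rules alone is reasonable. Relatedness must be assigned for every event and Protocol Appendix 1 repeats the obligation. Subjects are confined and questioned at least daily, data are source-verified and queries are to be resolved, so neither default should operate often. SAP 8.1.2 allows stated exceptions to its rule against imputation, and these are stated in advance. All events are listed, no inferential safety analysis is planned (SAP 8.6.6), and counting a missing assessment as related would report a judgement that nobody made.

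Most of this stands, and it limits the size of the point. The last argument is a good reason to prefer a missing row to counting the event as related. It applies equally to the SAP's rule, since not related is also a judgement that nobody made. Rarity does not argue for the favourable direction when a visible row costs one sentence.

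It can also be said that the dosing-day clause only formats onset after emergent status has been decided, so it cannot contradict the default. That is correct: the two sit uneasily for Day 1 but do not formally conflict.

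A reader might infer that the severity part of the emergent definition ("starts prior to dosing and increases in severity after dosing within each period") cannot be derived, because Protocol Appendix 1 tells sites to "record as a single event with the worst severity on the appropriate eCRF". The documents do not establish this. The case report form may date the worsening. It is not available here, and SAP 1 says that it was reviewed when the SAP was written. Appendix 1 also counts exacerbation of a pre-existing condition as an adverse event, so some worsening may be recorded separately.

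**Conclusion.** A minor improvement is warranted. Both defaults are plainly stated, both can only lower the counts or leave them unchanged, and the causality rule is out of step with the SAP's own treatment of missing severity and missing categorical data. Frequency is unknown and probably low. One subject with missing causality changes the treatment-related rate by at most 7.1 points for Treatment C, or about 0.7 points for A or B, under the assumptions above. Bioequivalence is unaffected.

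A reader might carry the 7.1 points over to the onset default. The documents do not support that. Treatment C is given only on Day 7, and a Day 7 date without a time falls after the first dose and is, by implication, attributed to that day's dose. The onsets that stay unresolved are a Day 1 date without a time, a partial date spanning Day 1, or a missing start. None can be identified as a Treatment C event.

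A reader might also link this to the start of non-serious event collection, which is enrollment in Protocol 7.2.1 and first study treatment in footnote j of the Appendix 9 schedule. Those texts do differ and should be reconciled, but that is a separate matter about the recording window.

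**What to change.** Amend SAP 8.6.1 in the current copy of the text, which is the one whose document history logs changes in 2022:

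1. Show emergent events with no causality assessment in a missing row of the treatment-related tables, as is done for severity. Counting them as related is an acceptable alternative.
2. Treat an event with unresolved onset as treatment-emergent unless the partial dates, or the investigator's answer on onset before the first dose, show that it began before the first dose.
3. Attribute an event dated on a dosing day without a time to that day's dose. Put any onset that cannot be placed in a period, whether wholly missing or partial, in a row for treatment not determined. This row is needed because the investigator's answer settles onset against the first dose only.

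The cost is about three SAP sentences and the matching table shells. No protocol amendment is needed for these changes. Emergent and treatment-related counts may be slightly higher. If the database is already locked, the same rows can be reported as a supplementary analysis, which SAP 1 allows if it is identified in the study report.
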